## Request for Expedited IRB Review Form attached

Human Subject Research: Human subject research means research involving interaction or intervention with living human beings or access to identifiable private information of living human beings.

**Research Plan:** The information requested in the Research Plan is designed to provide the IRB with the necessary information such that it can make the federally required determinations codified at 38 CFR Part 16, 21 CFR Parts 50, 54, & 56, and 45 CFR Part 46

The Research Plan is to be written so that the non-scientist/non-medical members of the IRB can understand the research proposed. Define all abbreviations and terms that are not part of common language.

**Version Date:** This should be updated subsequently with every modification to any part of the Research Plan. Any modification to this document, no matter how minor, must be reviewed and approved by the IRB prior to implementation. The Research Plan will be stamped with the date of IRB approval

## Section 2 – Research Sites and Sponsor

5. Please list all Research Sites in addition to Louis Stokes Cleveland DVA Medical Center (LSCDVAMC);

International studies when the PI is the Lead Investigator list the countries:

a. When study procedures including analysis of identifiable samples or data involving LSCDVAMC enrolled subjects will be conducted at any site other than the LSCDVAMC please provide the following:

Name and contact information for the site:

Describe the plan for communicating protocol amendments, reports of serious adverse events, reports of unanticipated problems involving risks to subjects or others, interim reports, and DSMB reports to external sites.

- \* When the LSCDVAMC is considered the coordinating center and the PI the lead investigator on cooperative research or a multi-center trial contact AO/Research [contact].
  - 6. Sponsor or other Support (list industry sponsor, government support, etc.): V.A. Merit Review

## Section 3 – Research Design and Procedures

7. Definitions- Provide a list of all abbreviations and specialized terms to be used in this document and their definitions:

| Abbreviations / Specialized Terms (Use the Enter key in this column to insert additional abbreviations and their definitions) | Definition                                |
|---|---|
| LSCDVAMC  | Louis Stokes Cleveland DVA Medical Center |
| FES   | Functional Electrical Stimulation         |
| SCI   | Spinal Cord Injury                        |
| UECU  | Universal External Control Unit           |
| US FDA  | US Food and Drug Administration           |
| RPE   | Rating of Perceived Exertion scale        |
| URS   | Usability Rating Scale                    |
| C-Fine  | Composite-Flat Interface Nerve Electrode  |
| DEXA  | Dual-energy x-ray absorptiometry          |
| ASIA  | American Spinal Injury Association        |
| SCI-QOL   | Spinal Cord Injury-Quality of Life        |

- 8. Provide a BRIEF SUMMARY of the background for this research. DO NOT CUT and PASTE paragraphs that do NOT summarize the background.
  - Include a critical evaluation of existing knowledge, and specifically identify the information gaps that your protocol is intended to fill.
  - Refer to appropriate citations in the scientific literature and include your references at the end of this section.
  - Include the rationale for conducting the research at the VA.

The overall goal of this project is to improve the functionality, physiological benefits, and safety of FNS systems that stimulate the trunk, hip and lower extremity muscles to restore standing function to individuals with paraplegia. Altering the pattern of activation of the knee extensor muscles promotes prolonged standing time so that users of neuroprostheses can accomplish activities of daily living that require standing for longer durations. Thus, increasing the health benefits associated with increased dosages of weight bearing. The optimal fatigue delaying stimulation regimes will be implemented clinically in 15 subjects to demonstrate the utility and generalizability of the approach.

Currently available FNS systems for standing utilize supra-maximal levels of constant stimulation at the hips and knees. This ensures the knees remain locked during standing, but at the cost of increased fatigue and reduced standing times. In a Phase II clinical trial conducted by our group, small number of the cohort of 18 implant recipients were able to achieve standing times exceeding 10 minutes but most users were limited to much shorter durations due to the rapid onset of muscle fatigue [1]. Standing times for the group averaged approximately 10 minutes with a median of only approximately 3 minutes. For the 11 subjects that continued to participate in the research program for at least two years after implantation, more than half never achieved standing times greater than 5 minutes. While there is no discernible relationship between standing time and factors such as injury level, degree of preserved sensation or time post-injury, the problem is especially pronounced in taller and heavier subjects. [2]

While the relatively short standing times achievable with continuous stimulation are sufficient for facilitating transfers and accomplishing some activities of daily living, many positive outcomes including the health benefits of weight bearing, swing-to gait, and the ability to participate in other important social, work and personal activities necessary to resume an active and independent lifestyle require durations longer than 5 minutes [3].

This project will determine the feasibility and performance of stimulation paradigms that exploit the ability of new multi-contact peripheral nerve electrodes to selectively activate individual portions of different muscles in order to prolong standing duration. Multi-contact nerve cuff electrodes such as the CWRU spiral and the Flat Interface Nerve Electrode (FINE) and the Composite-Flat Interface Nerve Electrode (C-FINE) have already been approved for chronic implantation as part of upper and lower extremity neuroprostheses by the USFDA and the IRBs of both the LSCDVAMC and MetroHealth Medical Center. This new project will continue to utilize these clinically proven technologies and apply their unique ability to efficiently and effectively activate independent motor unit pools within a muscle or independent synergists innervated by a common motor nerve.

- [1] V.K. Mushahwar, P.L. Jacobs, R.A. Normann, R.J. Triolo, and N. Kleitman, "New functional electrical stimulation approaches to standing and walking," j neural Eng, vol.4, pp.S181-97, 2007.
- [2] R.J. Triolo, S.N. Bailey, M.E. Miller, L. Rohde, J. Anderson, J.A. Davis, J.J. Abbas, L.A. Diponio, G.P. Forrest, D.R. Gater, L.J. Yang, "Longitudinal performance of a surgically implanted neuroprosthesis for lower extremity exercise, standing, and transfers after spinal cord injury, *Archives of Physical Medicine and Rehabilitation*. 93(5):896-904, 2012.
- [3] J.J.Eng, S.M.Levins, A.F.Townson, D.Mah-Jones, J.Bremner, and G.Huystion, "Use of prolonged standing for individuals with spinal cord injuries, "Phys Ther, vol.81,pp.1392-9, 2001.
- 9. Provide a BRIEF SUMMARY of the purpose and scientific rationale for this research. DO NOT CUT and PASTE paragraphs that do NOT summarize the purpose and scientific rationale.
  - State clearly, in terms a non-scientist/non-medical person can comprehend, what you expect to learn from the study and the specific hypothesis (es) to be tested.
  - The objectives should be stated in such a way that the reader can determine the appropriateness of the study design.

Neuroprostheses for standing after SCI currently rely on continuous activation of the hip and knee extensor muscles, which results in rapid fatigue and ultimately compromises elapsed standing time. The primary objective of this study is to improve the performance of neuroprostheses for standing by developing and implementing advanced stimulation paradigms that use multi-contact peripheral nerve electrodes to delay fatigue onset and prolong standing duration. The new stimulation paradigms will take advantage of the ability of multi-contact nerve cuff electrodes to selectively activate independent portions of a muscle, or independent muscles that perform the same action. Such a capability will allow one or more muscles (or parts of the same muscle) to rest while the others continue to contract to keep the knee extended and the user upright. Stimulation waveforms that alternate activation to multiple muscles performing the same function, rather than continuously activate the entire muscle group constantly, should allow muscles to rest and recover from fatiguing contractions.

In addition to these important clinical benefits, the project is also of high impact and significance because the methods to be developed will not be specific to any single electrode technology or stimulation system. Any clinical or therapeutic application that requires a sustained muscular contraction or the production of constant joint torques for prolonged periods of time will benefit from the successful completion of this project.

#### This project is significant because it will:

- a) Extend the functionality of standing neuroprostheses and enable more complex and time consuming activities of daily living
- b) Allow neuroprosthesis users to receive the full health benefits of weight bearing and upright mobility
- c) Improve the overall safety of neuroprostheses for standing.

The Specific aims of this study are:

- 1) Establish the clinical feasibility of new stimulation paradigms (such as carousel, interleaved and sum of phase-shifted sinusoid among others) for prolonged muscle force production in subjects with SCI.
- 2) Automate the tuning of the fatigue delaying stimulation paradigms to maximize performance and generate objective methods for ensuring optimal clinical performance.
- 3) Demonstrate improved functional outcomes of the advanced fatigue-delaying stimulus schemes in terms of standing duration, body weight distribution and subjective and objective measures of stability.

#### THE HYPOTHESES TO BE TESTED ARE:

- The knee joint torques generated by fatigue delaying stimulation paradigms will be sufficient to keep the knees locked during standing for at least 10 minutes. This will be tested by tracking how long the knee can produce an extension torque on the dynamometer that exceeds a threshold set for each subject based on their body weight. [5.]
- Standing with fatigue delaying stimulation paradigms will be more stable and of longer duration
  than constant stimulation. This will be tested by recording the elapsed standing times before
  system users are required to sit due to fatigue of the quadriceps muscles for each of the
  advanced stimulation waveforms, as well as by monitoring variations in knee angle and
  subjective impressions of stability while standing.
- Clinical performance of the fatigue delaying stimulation paradigms will be stable over time. This
  will be tested by repeating the tuning procedures and comparing the optimal parameters over
  time, repeating dynamometer testing of the same stimulus paradigm at various time intervals,
  and repeating stand-to-fatigue, body weight distribution and stability tests in the laboratory.
- Objective optimization of control parameters will lead to longer sustained contractions before
  fatigue. This will be tested by comparing the knee extension torque produced by hand tuning the
  stimulation paradigms to the outcome applying the automated and objective optimization
  process for setting up stimulus parameters. These experiments can be performed primarily on
  the dynamometer and verified during standing in the laboratory.

## 10. Describe the means of analyzing the data and evaluating the results.

- State the anticipated methods to be used for analysis and interpretation of the data.
- The methods must compliment the design of the study and the nature of the data which is being collected.

This study takes the form of a case series and employs the principles of single-subject research design. Each subject acts as his or her own concurrent (differences among stimulation paradigms for the individual at the same time interval) and longitudinal (initial post-exercise and training measurement versus follow-up values) controls. Primary statistical analyses will be in

comparison to the continuous stimulation case and will be performed on each subject individually. The effect sizes for these analyses were estimated using data obtained from existing 8-channel users and assuming a power level of 80%.

- 1. The longitudinal stability of the optimal stimulation parameters (pulse width and amplitudes) to ensure selective and non-overlapping activation of different muscles with each contact within the nerve cuffs will be assessed via a two-tailed t-test between initial and follow-up measurements.
- 2. Differences among the fatigue-delaying stimulation paradigms (carousel, interleaved, sum of phase-shifted sinusoid) and in comparison to continuous stimulation in terms of biomechanical measures of fatigue (T50, T0.21) and isometric strength will be determined by ANOVA performed on repeated measures of the outcome variables at each measurement interval.
- 3. Standing performance in terms of elapsed standing time and body weight distribution on the arms and legs will be compared across stimulation paradigms for each subject via ANOVA.
- 4. Standing stability in terms of variations in knee joint angle and location of body center of mass while standing with various stimulation paradigms will be assessed via ANOVA. The Wilcoxon Ranked Sum Test will be applied to the seven point ordinal data related to the subjective impressions of stability.

Tests will nominally be repeated three times in random order and the resulting body weight distribution and elapsed standing durations will be compared via ANOVA to determine the relative performance of each stimulation paradigm.

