## 11. Provide a BRIEF DESCRIPTION of how the estimated number of study subjects needed for this research was determined

- If this is a quantitative study provide the method of determining sample size estimates.
- If multiple studies are planned provide a power analysis or justification for each one.

The number of new subjects (15) to be enrolled in this project and receive implanted neuroprostheses was based on the effect size and variability observed in previous measurements of the outcomes of interest (elapsed standing time, body weight support, knee extension torque) and an assumed power level of 80%. The timing of recruitment and enrollment is based on the time required to fabricate implanted electrodes and stimulators, as well as the time required for implanting, training and testing the subjects who receive the devices. In addition, 10 existing subjects who had already received their implanted systems while enrolled in other approved protocols will be eligible to volunteer for the testing and experimentation portion of the study.

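### Hypothesis 2 is tested one subject at a time, with no primary outcome, no alpha and no rule or group-level test that turns individual results into a general conclusion

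*Combined protocol and SAP*

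**What the plan says.** Item 10 describes the design: "This study takes the form of a case series and employs the principles of single-subject research design". Primary analyses are to be in "comparison to the continuous stimulation case and will be performed on each subject individually". Analysis 3 repeats this for the standing test: "elapsed standing time and body weight distribution on the arms and legs will be compared across stimulation paradigms for each subject via ANOVA". Analysis 4 adds knee-angle variation and centre-of-mass location by ANOVA, and a seven-point stability rating by a Wilcoxon test. Tests are nominally repeated three times in random order.

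The claims are wider than one subject. The second hypothesis under item 9 reads "Standing with fatigue delaying stimulation paradigms will be more stable and of longer duration" than constant stimulation. It names three measures: standing time, knee-angle variation and subjective stability. Item 8 says the optimal regimes "will be implemented clinically in 15 subjects to demonstrate the utility and generalizability of the approach".

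Item 11 gives 15 new subjects, and adds that "10 existing subjects who had already received their implanted systems while enrolled in other approved protocols will be eligible to volunteer" for the testing portion, so 15 to 25 people may be analysed. Item 11 lists three outcomes of interest without ranking them. Item 13 calls a stand of more than 10 minutes functionally relevant, but that threshold applies to a single stand and is not tied to any test. The plan contains no alpha, multiplicity rule, required number of positive subjects or group-level test.

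**The concern.** The stated analysis returns 15 to 25 sets of p-values, several per subject, and stops there. Hypothesis 2 and the generalizability aim are statements about users as a group, and nothing connects the two. If a few subjects show significantly longer or steadier standing, the plan gives no way to say whether that supports the hypothesis or is about what chance would produce. The choice of what counts would be made after the results are known, and the false-positive risk depends heavily on that choice.

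**Working it through.** **The plan's own figure.** Item 11 rests 15 subjects on 80% power but gives no effect size, SD, alpha or test, so the number cannot be reproduced. Fifteen subjects give 80% power in a two-sided 0.05 paired test for a standardized difference of 0.78. That does not describe the per-subject tests. There, a contrast of three repeats with three (8 df) needs a difference of about 2.6 within-subject SDs for 80% power.

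**Inputs.** N = 15 or 25 (item 11). Four conditions: three paradigms and continuous stimulation (item 13, Testing and Experimentation). Three repeats (item 10). Four ANOVA outcomes: standing time, body weight distribution, knee-angle variation and centre of mass (item 10, analyses 3 and 4). Assumptions: two-sided alpha 0.05 (0.01 also shown), no effect in anyone, independent subjects, normal errors, one measurement interval.

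**1. Standing time, any direction.** P(at least one subject) = 1 − (1 − α)^N.
- 1 − 0.95^15 = 0.537; 1 − 0.95^25 = 0.723.
- At 0.01: 1 − 0.99^15 = 0.140; 1 − 0.99^25 = 0.222.

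**2. Standing time, favourable direction.** Simulation of the four-by-three layout requires a significant F (3 and 8 df) and then a significantly longer stand on some paradigm than on continuous (unadjusted t, 8 df). The rate is 0.0216 per subject.
- 1 − 0.9784^15 = 0.279; 1 − 0.9784^25 = 0.421.
- Repeat simulations gave 27–29% and 41–43%.

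**3. Four standing outcomes, any significant ANOVA.**
- Independent: 1 − 0.95^60 = 0.954; 1 − 0.95^100 = 0.994.
- Correlation 0.8 (simulated): 0.87 and 0.97.
- Favourable direction only, F first, correlation 0 to 0.8: 0.60–0.74 and 0.78–0.89.
- Independent at 0.01: 1 − 0.99^60 = 0.453; 1 − 0.99^100 = 0.634.

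**4. Duration and objective stability in the same subject.** The ANOVA for standing time and the ANOVA for knee angle or centre of mass must both be significant.
- Independent: 0.05 × (1 − 0.95²) = 0.004875 per subject, giving 0.071 and 0.115.
- Correlation 0.8: 0.31 and 0.46.
- If the same paradigm must also be favourable on both: 0.01–0.14 and 0.02–0.23.

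**5. Subjective rating.** If the rank-sum test compares three ratings with three, its smallest two-sided p is 2/C(6,3) = 2/20 = 0.10. It cannot reach 0.05 in a single subject, so it adds no false positives at that level and cannot support the hypothesis there either.

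**6. Two ways to reach a general conclusion.** Suppose one paradigm lengthens standing by 1 within-subject SD on average, with N = 15.
- Count rule: at least 3 positive subjects by one-sided Dunnett at 0.05. Under no effect, P(Bin(15, 0.05) ≥ 3) = 0.036.
- Group test: a difference of two three-repeat means has variance 2/3, so d = 1/√(2/3 + τ²), where τ is the between-subject SD of the effect. Power is from the noncentral t on 14 df, one-sided at 0.05/3.

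| τ | Count rule met | Group test, d | Group test, power |
|---|---|---|---|
| 0 | 53% | 1.22 | 99% |
| 0.5 | 64% | 1.04 | 94% |
| 1 | 81% | 0.77 | 73% |

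With two-sided 0.05/3 the group-test power is 97%, 89% and 62%.

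**The case against.** The strongest reply is that this is a declared case series with single-subject design and a feasibility aim. In that setting, inference within each person is legitimate, and no passage says that one significant subject would prove hypothesis 2. That stands: the error rates above belong to decision rules the plan never adopts. But item 10 calls these the primary statistical analyses, item 9 lists hypotheses to be tested, and item 8 claims generalizability. A link to those claims is still needed.

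Four stronger readings are tempting and not supported.
- **Seven outcomes, so a false positive is practically certain.** Seven is the count of ANOVA outcomes across analyses 2 to 4. Three of them are dynamometer measures (T50, T0.21 and isometric strength) that hypothesis 2 does not name.
- **No protection across paradigms.** Each ANOVA is already a global test of the four conditions. This is why the directional standing-time figures are 28% and 42%.
- **The data cannot separate a paradigm that helps some users from one that helps none.** They can, because the number of positive subjects is informative. What is missing is a prespecified rule.
- **A required count, such as 3 of 15, would be enough.** It rejects only the statement that nobody benefits, possibly with 12 subjects negative and each positive on a different paradigm. It also says nothing on stability. When effects vary widely between subjects it is met more often than the group test, but it answers a different question.

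**Conclusion.** The concern holds as a gap in the decision rule. Hypothesis 2 has per-subject primary tests, no designated primary outcome, no alpha, and no group-level test or rule leading to the general claim. With 15 and 25 subjects, the chance of at least one false-positive subject is 54% and 72% for a standing-time ANOVA in any direction, and 28% and 42% when a favourable contrast is also required. Over four independent standing outcomes it is 95% and 99%. If duration and objective stability must coincide in one subject, it falls to 7–31% and 11–46%. These figures assume two-sided 0.05, three repeats and no true effect, and a stricter alpha lowers them. A reader might infer that chance findings are close to certain under the plan. The documents do not support that, because they do not say what would count as success. That the risk runs from below 10% to above 90% on an unstated choice is the defect.

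**What to change.** In item 10:

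1. Name elapsed standing time as the primary outcome for hypothesis 2, and state alpha and whether tests are one- or two-sided.
2. Within each subject, compare the three paradigms with continuous stimulation by Dunnett's procedure. Report these as individual-level findings, with the number of positive subjects.
3. Base the general conclusion on one group-level analysis of the same data. Take each subject's mean paradigm-minus-continuous difference in standing time and test it across subjects by a paired analysis, or use a mixed model with subject as a random effect. Adjust for three paradigms, and state whether existing recipients are included with the 15 new subjects.
4. Report knee-angle variation, centre of mass, body weight distribution and the subjective rating as supportive, with intervals. Limit the stability part of the conclusion accordingly.

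The cost is a few sentences of text, stricter critical values (within a subject, two-sided on 8 df, from 2.31 to about 2.87 by simulation) and secondary status for the other outcomes. No new subjects, visits or data are needed.

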#### Testing and Experimentation (Phase III):

Once training is completed, the subject will commence with the testing phase to assess the performance of the implanted system.

Implementation of the fatigue delaying paradigms is essentially a three-step process.

- 1.) Stimulation parameters must be chosen to produce strong muscle contractions with little or no overlap in the populations of motor units activated. This step will be accomplished with the subject positioned in a dynamometer while stimulation parameters are varied by a computer-controlled optimization algorithm to create non-overlapping recruitment curves. [6].
- 2.) Using the values that specify non-overlapping stimulation as an upper limit, patterns must be tuned to produce the desired profile of joint torque, such as ramping up, plateau time, and ramping down for carousel stimulation, or sinusoidal oscillation frequency and pulse width values for the SOPS paradigm. For the carousel and SOPS paradigms, it is important to ensure that the maximum joint torques generated by stimulating through individual contacts are balanced and roughly equivalent to each other to avoid ripple (jitter or oscillations) in the output when they are combined.
- 3.) Joint torque will be recorded on the dynamometer during each stimulation pattern and ripple will be quantified to ensure that a constant contraction is achieved.

These three steps can be completed in approximately five two-hour long sessions.

Biomechanical Tests Strength and Endurance: Once stimulation patterns have been hand-tuned to produce strong, low-ripple contractions for each of the fatigue delaying stimulation regimes, tests of their functional impact on fatigue will be performed. To quantify the rate of fatigue of each paradigm isometric fatigue tests will be performed on the dynamometer with the knee held in 20° of flexion. Each fatigue test will consist of approximately 30 minutes of stimulation with a particular paradigm. Fatigue tests for all four conditions (SOPS, carousel, interleaved and baseline continuous stimulation) will be repeated for both legs nominally three times in random order for each subject, with never more than one fatigue test per leg per day.

Standing Time and Body Weight Distribution:

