#### Discharge and Follow-up:

A user questionnaire will be administered prior to discharge to home to assess subjective satisfaction with the system. [7,8]. After discharge to home, medical conditions will be monitored on an ongoing basis via regular telephone or other means of electronic contact. While at home, the external controller for the implanted system will monitor patterns of usage and record the number and length of time each exercise or functional pattern is active. External controllers will be returned and exchanged for replacement units in a preventative maintenance program, at which time usage data will be downloaded and stored for later analysis [4].

Self-report of frequency and severity of pressure injuries, spasms, urinary tract infections and other medical conditions are monitored on a continual basis. Subjects may be requested to repeat the tests described above at follow-up intervals of approximately 6 to 12 and 18 to 24 months post-implantation. Data from the system monitor built into the External Control Unit will be downloaded during follow-up intervals.

Biomechanical tests of strength and endurance with continuous stimulation and each of the fatigue delaying stimulus paradigms will be repeated on the dynamometer. Elapsed standing times, body weight distribution and stability assessments may also be repeated as described above. Consistency of the stimulus parameters and biomechanical and clinical measures of standing performance will be assessed by comparing these follow-up results to baseline data pre-discharge.

Long term follow-up will include reapplication of the user questionnaire, and repeated measures of the medical and technical evaluations performed at intake. This may include repeat physical examinations, motor and sensory evaluation, bone density assessments and AP/Lateral images of the joints to document any changes due to weight bearing. The integrity and stability of the implanted components will be assessed through repeated measurements of surface potentials and

recruitment properties. Electrode performance will be evaluated by conducting standardized biomechanical measurements including stimulus thresholds and maximal stimulated manual muscle grades, in addition to the dynamometer and clinical tests of standing performance applied at the short-term follow-up interval. The SCI-QOL will be repeated at follow-up intervals after rehabilitation and training is completed for comparison against baseline ratings.

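### Analysis 1 tests for a difference with no tolerated change, so it can show drift in the stimulation parameters but cannot support their stability

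*Combined protocol and SAP*

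**What the plan says.** Item 9 lists among the hypotheses to be tested: "Clinical performance of the fatigue delaying stimulation paradigms will be stable over time". Three strands of evidence follow: retuned parameters, repeat dynamometer tests, and repeat standing tests. This point concerns the first only, which "will be tested by repeating the tuning procedures and comparing the optimal parameters" over time.

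Item 10, analysis 1, is the stated analysis for that strand. Longitudinal stability of pulse width and amplitudes "will be assessed via a two-tailed t-test between initial and follow-up measurements". The same sentence gives the purpose of the parameters: "to ensure selective and non-overlapping activation of different muscles with each contact within the nerve cuffs".

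Item 13, Testing and Experimentation (Phase III), describes the same aim at initial tuning. Step 1 seeks "strong muscle contractions with little or no overlap in the populations of motor units activated". Step 2 begins "Using the values that specify non-overlapping stimulation as an upper limit". Neither step puts a number on overlap, and neither is linked to the t-test.

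On follow-up, Item 13, Discharge and Follow-up, says "Subjects may be requested to repeat the tests described above at follow-up intervals". It then says without qualification that the dynamometer tests will be repeated and that consistency of the stimulus parameters will be assessed against pre-discharge data. The standing tests are again only possible repeats.

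**The concern.** In analysis 1 the claim to be supported sits in the null hypothesis. A significant result contradicts stability. A non-significant result says only that drift was not detected, which can happen because there was none or because the data were too few or too variable to show it. With no tolerated change stated, nothing separates the two.

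At stake is the conclusion on a named hypothesis. If the report called parameters stable because the test was not significant, that conclusion would be easiest to reach where the evidence was thinnest. The remedy also depends on timing: a tolerated change chosen after follow-up values have been seen would carry little weight.

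**Working it through.** **1. Does the plan's sample size cover this analysis?** Item 11 gives 15 new subjects at an assumed 80% power. The figure cannot be reproduced, because alpha, effect size and SD are not given. The outcomes it names are standing time, body weight support and knee extension torque; stimulation parameters are not among them. Item 10's general statement about 80% power adds no tolerated change.

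**2. What enters the test?** The documents do not say whether the test is paired, whether it is run per subject or pooled, how contacts and legs within a subject enter, or how many determinations are made per visit. The nominal three repeats in Items 10 and 13 belong to the standing and fatigue tests. Item 10 applies analysis by individual subject to the primary comparisons, without saying that this covers analysis 1. Both readings are therefore illustrated. Every alpha, replicate count, SD and margin below is assumed.

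**3. One subject, n values at each visit, drift of d within-visit SDs.** Two-sample t-test, two-sided alpha 0.05, df = 2n − 2, noncentrality = d × √(n/2). P(missed) = F(t_crit) − F(−t_crit), with F the noncentral t distribution. At d = 2 and n = 3: noncentrality = 2 × √1.5 = 2.449, df = 4, t_crit = 2.776, P(missed) = 0.537. At d = 2 and n = 8: noncentrality = 2 × √4 = 4, df = 14, t_crit = 2.145, P(missed) = 0.040.

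| Values per visit | No drift: non-significant | 1 SD drift missed | 2 SD drift missed |
|---|---|---|---|
| 3 v 3 | 95% | 84% | 54% |
| 5 v 5 | 95% | 71% | 21% |
| 8 v 8 | 95% | 54% | 4% |

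With 3 v 3, non-significance is only 0.95 / 0.537 = 1.8 times as likely under no drift as under a 2 SD drift. With 8 v 8 the ratio is 0.95 / 0.040 = 24. The same verdict of 'not significant' therefore means very different things, and the plan does not say which case applies.

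**4. Pooled over subjects, one change per subject.** Paired test on the log scale, noncentrality = |ln 0.7| × √n / SD = 0.357 × √n / SD, with assumed SD of log change 0.31 to 0.43. A true 30% fall is missed 50–70% of the time at n = 5, 20–48% at n = 8, 1.5–15% at n = 15 and at most about 2% at n = 25. The last figure takes the 15 new subjects plus Item 11's "10 existing subjects who had already received their implanted systems while enrolled in other approved protocols will be eligible to volunteer". Both 15 and 25 are upper bounds. Item 13, Surgical Procedures and Implantation, allows intramuscular electrodes in subjects unsuited to cuffs, and no section says that the existing recipients have multi-contact cuffs or a comparable initial tuning. High pooled miss rates therefore need few subjects or a small drift. At any n, though, there is no limit against which to read non-significance.

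**5. What an interval rule would deliver.** Call the parameters stable only if the 90% confidence interval lies inside ± margin. At a true change equal to the margin, the chance of wrongly concluding stability is at most 5%. Within one subject the half-width is about t(0.95, df) × √(2/n) SDs: 2.132 × √(2/3) = 1.74 for 3 v 3, and 1.761 × √(2/8) = 0.88 for 8 v 8. Power at zero true change:

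| Values per visit | Margin 1 SD | Margin 2 SD |
|---|---|---|
| 3 v 3 | 3% | 38% |
| 8 v 8 | 23% | 97% |

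Power of 80% needs 18 values per visit for a 1 SD margin and 6 for 2 SD. Pooled, with an assumed margin of ±0.357 on the log scale (70% to 143%) and the SDs of step 4, power is 16–43% at n = 5, 84–99% at n = 15 and 98–100% at n = 25.

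**The case against.** The strongest reply is that the plan never equates a non-significant test with stability. That is true, and a reader who infers that it does goes further than the text. The gap remains: the plan gives no other rule by which analysis 1 could support the hypothesis.

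Second, the hypothesis is about clinical performance, and the dynamometer and standing strands bear on it more directly. Long-term follow-up also repeats recruitment properties and stimulus thresholds. This stands, and it limits the point to one strand. It does not follow that the whole stability hypothesis is untestable.

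Third, a reader might infer that follow-up is optional and few subjects will return. The documents are mixed: the general sentence is permissive, the dynamometer repeats and the parameter comparison are stated as planned, and willingness to comply with follow-up is an inclusion criterion in Item 30. The n = 5 and n = 8 figures show what would happen if few returned; they do not predict that few will.

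Fourth, a margin is not simply there to be read off. If recruitment itself changes, the initial curves predict later overlap only if their shape is preserved, which is not stated. Step 2 treats the non-overlap values as an upper limit, which is one-sided. Pulse width and amplitude may also trade off against each other, so separate limits for each may not map to overlap. This stands, and the fix allows for it.

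**Conclusion.** The point holds for analysis 1 as written: it can contradict the parameter strand of the stability hypothesis but cannot support it. This follows from the form of the test and the absence of any criterion, and does not depend on the assumed numbers. Those show only size: within one subject a 2 SD drift is missed 54% of the time at 3 v 3 and 4% at 8 v 8. The same data could support stability if a tolerated change were set in advance.

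A reader might also infer from the pooled SDs that 25–41% of subjects would truly lie beyond a 70–143% margin even with zero mean change. The documents give no SD, and that calculation treats all observed spread as real change. If half the variance were tuning and measurement error, the share would be 10–24%: 2 × [1 − Φ(0.357 / (SD/√2))] with SD 0.31 and 0.43. No figure for true individual drift can be supported.

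It is worth correcting before follow-up data are examined. It does not touch the primary comparison with continuous stimulation.

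**What to change.** In Item 10, analysis 1, replace the significance test with the estimated change from initial to follow-up and its 90% confidence interval.

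- Report it for each subject. If results are pooled, use one value per subject or a mixed model with subject as a random effect, so that contacts and legs are not counted as independent. Describe a pooled result as average stability only.
- Before follow-up data are examined, have the investigators fix a tolerated change and justify it by the plan's own criterion of selective, non-overlapping activation. Initial recruitment curves may inform it. It may be one-sided, or set on overlap itself rather than on each parameter.
- Conclude 'stable' only if the interval lies inside the margin, 'changed' if it lies wholly outside, and 'inconclusive' otherwise. State that p > 0.05 will not be read as stability.
- State the number of determinations per contact and visit, which subjects and electrode types are included, and the follow-up interval to which the conclusion applies.
- If subjects within the margin are counted, give an exact 95% interval and note that the count includes measurement error. The counts are imprecise: 13 of 15 gives 60–98%, and 5 of 5 gives 48–100%.

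The cost is analysis wording and agreement on a numeric limit. No extra visits are needed if inconclusive per-subject results are accepted, and with few values per visit there will be many. Narrowing them means more determinations, which is a real burden: Item 13 puts the three-step setup at about five two-hour sessions.
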